16.8 Inclusion of Women and Minorities

16.81 This study will be available to all eligible patients, regardless of race, or ethnic origin.

16.82 There is no information currently available regarding differential effects of this regimen in subsets defined by race, or ethnicity, and there is no reason to expect such differences to exist. Male breast cancer is a relatively rare entity in whom APBI would not be appropriate therapy and male gender is an exclusion criteria. Although the planned analysis will, as always, look for differences in treatment effect based on racial groupings, the sample size is not increased in order to provide additional power for subset analyses.

16.83 The geographical region served by the Mayo Clinic, has a population which includes approximately 5% minorities. We expect about 5% of patients will be classified as minorities by race and about 100% of patients will be women.

Accrual Estimates by Gender/Ethnicity/Race

Ethnic Category	Accrual Targets		
	Sex/Gender		
	Females	Males	Total
Hispanic or Latino	2	0	2
Not Hispanic or Latino	23	0	23
Ethnic Category: Total of all subjects	25	0	25
American Indian or Alaskan Native	1	0	1
Asian	0	0	0
Black or African American	1	0	1
Native Hawaiian or other Pacific Islander	0	0	0
White	23	0	23
Racial Category: Total of all subjects	25	0	25

Ethnic Categories: **Hispanic or Latino** – a person of Cuban, Mexican, Puerto Rican, South or Central American, or other Spanish culture or origin, regardless of race. The term “Spanish origin” can also be used in addition to “Hispanic or Latino.”

Not Hispanic or Latino

Racial Categories:	
American Indian or Alaskan Native – a person having origins in any of the original peoples of North, Central, or South America, and who maintains tribal affiliations or community attachment.
 
Asian – a person having origins in any of the original peoples of the Far East, Southeast Asia, or the Indian subcontinent including, for example, Cambodia, China, India, Japan, Korea, Malaysia, Pakistan, the Philippine Islands, Thailand, and Vietnam. (Note: Individuals from the Philippine Islands have been recorded as Pacific Islanders in previous data collection strategies.)
 
Black or African American – a person having origins in any of the black racial groups of Africa. Terms such as “Haitian” or “Negro” can be used in addition to “Black or African American.”
 
Native Hawaiian or other Pacific Islander – a person having origins in any of the original peoples of Hawaii, Guam, Samoa, or other Pacific Islands.
 
White – a person having origins in any of the original peoples of Europe, the Middle East, or North Africa.

---------------------------	---

17.0 Pathology Considerations/Tissue Biospecimens

17.1 Summary Table of Research Tissue Specimens

	Mandatory or Optional	Type of Tissue to Collect	Block, Slides, Core, etc. (# of each to submit)	Process at Site? (Yes or No)
Diagnostic	Mandatory	Formalin Fixed and Flash Frozen tumor	See below	Yes
Definitive surgery	Mandatory	Formalin Fixed and Flash Frozen tumor	See below	Yes

Tissue requirements:

Paraffin blocks: Two (2) of the initial diagnostic core biopsy and two (2) blocks of the cancer at the time of surgery, if available.

Alternate to paraffin blocks:

Two 2 mm core sampling of the existing tumor block from an area rich in tumor cells or a similar size fragment cut from the original block

Flash frozen tissue at the time of surgery: One 18g needle core of the initial diagnostic core biopsy and a 25-50mg tissue sample of the cancer at the time of surgery, if available.

We will send 25 mgs of the tumor to RST. We will send 25-50 mgs of the tumor and sentinel lymph node tissue to RST, if available.

17.2 Flow cytometry

For formalin fixed tissue samples excess paraffin is removed with a scalpel from either side of 40-60um scrolls then processed according to our published methods. Briefly each sectioned piece is collected into individual microcentrifuge tubes then washed three times with 1 ml Xylene for 5 minutes to remove remaining paraffin. Each sample is rehydrated in sequential ethanol washes (100% 5 minutes x2, then 95%, 70%, 50% and 30% ethanol) and washed 2 times in 1ml 1 mM EDTA pH 8.0. A 1 ml aliquot of 1 mM EDTA pH 8.0 is added to the samples and incubated at 95°C for 80 minutes to facilitate the removal of protein cross-links present in FFPE tissue. Samples are then cooled to room temperature for \geq 5 minutes, followed by addition of 300 ul PBS pH 7.4 and gentle centrifugation for 2 minutes at 3.6 x g. The supernatant is carefully removed and the pellet washed three times with 1 ml PBS pH 7.4/0.5mM CaCl₂ to remove EDTA. Each sample is digested overnight (6-17 hours) in 1ml of a freshly prepared enzymatic cocktail containing 50 units/ml of collagenase type 3, 80 units/ml of purified collagenase, and 100 units/ml of hyaluronidase in PBS pH 7.4/0.5mM CaCl₂ buffer. Following overnight digestion 500 ul NST is added to each sample to facilitate pelleting. Samples are centrifuged for 5 minutes at 3000 x g, after which pellets are resuspended in 750 ul of NST/10% fetal bovine serum and then passed through a 25 G needle 10-20 times.

Prior to sorting biopsies (formalin fixed or flash frozen) are minced in the presence of NST buffer and DAPI according to published protocols. Each sample is filtered through a 35 um mesh and collected into a 5 ml Polypropylene round bottom tube. The mesh is

rinsed with an additional 750 ul of NST/10% fetal bovine serum and placed on ice while processing remaining samples. The total volume in the tube for each sample is approximately 1.5 ml. An equal volume of 20ug/ml DAPI is added to each tube to achieve a final concentration of 10ug/ml DAPI for flow sorting with a BD Influx cytometer with ultraviolet excitation (Becton-Dickinson, San Jose, CA). The optimal settings for sorting FFPE samples with the Influx sorter are as follows: Drop formation was achieved with piezzo amplitude of 6-10 volts and a drop frequency of 30 khertz. The sort mode is set to purity yield with a drop delay of 31.5-32. Sheath fluid pressure was typically 17-18 psi with a 100 um nozzle. For single parameter DNA content assays DAPI emission is collected at >450nm. DNA content and cell cycle were then analyzed using the software program MultiCycle (Phoenix Flow Systems, San Diego, CA). All flow sorting will be done in the [name] laboratory located in the Collaborative Research Building on the MCA Scottsdale campus.

17.3 DNA extraction

DNA from sorted nuclei is extracted using an amended protocol from QIAamp® DNA Micro Kit from Qiagen (Valencia, CA). Briefly each sorted sample is resuspended in 180ul buffer ATL and 20ul proteinase K (20mg/ml) then incubated for 3 hours at 56°C for complete lysis. Samples are bound and washed according to QIAamp® DNA Micro Kit instructions, eluted into 50ul of H2O, then precipitated overnight with 5ul 3 M sodium acetate and 180 ul 100% EtOH. Each sample is then centrifuged for 30 minutes at 20,000 x g, washed in 1 ml of 70% EtOH for 30 minutes at 20,000 x g. The samples are carefully decanted and the DNA pellet is dried by speed vacuum then resuspended in a small volume (e.g. 10-50ul) of H2O for final concentrations suitable for accurate quantitation. All DNA extractions will be done in the [REDACTED].

17.4 Exome capture and sequencing

For each patient we will prepare sufficient DNAs from each sorted tumor population, as well as a patient matched control sample, for exome sequencing. Residual DNAs will be stored at MCA for future studies. All sequencing will be done within Mayo Clinic Medical Genome Facility (MGF) using established protocols for whole exome analysis. Briefly, whole exon capture is carried out using the protocol for Agilent's SureSelect Human All Exon 71 MB v6 kit. 500 ng of the prepped library is incubated with whole exon biotinylated RNA capture baits supplied in the kit for 24 hours at 65 °C. The captured DNA: RNA hybrids are recovered using Dynabeads MyOne Streptavidin T1 (Dynal). The DNA is eluted from the beads and desalting using purified using Ampure XP beads (Agencourt). The purified capture products are then amplified using the SureSelect Post-Capture Indexing forward and Index PCR reverse primers (Agilent) for 12 cycles. Libraries are loaded onto paired end flow cells at concentrations of 4-5 pM to generate cluster densities of 600,000-800,000/mm² using the Illumina cBot and HiSeq Paired end cluster kit version 3. The flow cells are sequenced as 101 X 2 paired end reads on an Illumina HiSeq 4000 using TruSeq SBS sequencing kit version 3 and HiSeq data collection version 1.4.8 software. Base-calling is performed using Illumina's RTA version 1.12.4.2

18.0 Records and Data Collection Procedures

18.1 Submission Timetable

Initial Material(s)

CRF	Treatment (Compliance with Test Schedule Section 4.0)
Institutional Contacts	
Patient Eligibility	
Demographics	
On-Study	≤2 weeks after registration
Pathology of Ipsilateral Breast	
Adverse Events- Baseline	
Patient Status: Baseline	
Patient Assessment	
	*6 months after accrual
Off Treatment	Submit ≤2 weeks after registration if withdrawal/refusal occurs prior to beginning protocol therapy

Test Schedule Material(s)

CRF	End of Treatment	12 weeks post-RT / Observation Phase ⁴	Event Monitoring ⁵
Radiation Therapy	X		
Radiation Lumpectomy Therapy	X		
Patient Assessment	X	X	
Adverse Events Solicited	X	X	
Adverse Events: Other	X ²	X ²	
Off Treatment	X ²	X ²	
Patient Status Form	X	X	X
Specimen Submission: Tissue (Recurrence)		X ²	
Consent Withdrawal	X ²	X ²	
Lost to Follow-up	X ²	X ²	
Breast Radiotherapy Questionnaire ³	X	X	

- ¹ Complete at each evaluation during Active Treatment (see Section 4.0).
- ² When applicable
- ³ Survey will need to be entered manually if has not alternately been scanned or entered electronically
- ⁴ Active monitoring observation phase, Day 15 (+/- 3 days), D90 (+/- 1 month), D180 (+/- 2 months), D365 (+/- three months), annually for 4 years (+/- 6 months, total 5 years follow-up). If patient progresses within observation, they will move to the event monitoring phase where they will be followed until 5 years of follow-up information has been completed from the end of treatment time point.
- ⁵ If patient has a recurrence prior to being off radiation therapy for 5 years, continue to follow yearly.

18.2 Data Handling and Record Keeping

18.21 Confidentiality

Information about study subjects will be kept confidential and managed according to the requirements of the Health Insurance Portability and Accountability Act of 1996 (HIPAA). Those regulations require a signed subject authorization informing the subject of the following:

- What protected health information (PHI) will be collected from subjects in this study
- Who will have access to that information and why
- Who will use or disclose that information
- The rights of a research subject to revoke their authorization for use of their PHI.

(This information is contained within the Mayo IRB Informed Consent Template Section 14)

In the event that a subject revokes authorization to collect or use PHI, the investigator, by regulation, retains the ability to use all information collected prior to the revocation of subject authorization. For subjects that have revoked authorization to collect or use PHI, attempts should be made to obtain permission to collect at least vital status (long term survival status that the subject is alive) at the end of their scheduled study period.

18.22 Source Documents

Source data is all information, original records of clinical findings, observations, or other activities in a clinical trial necessary for the reconstruction and evaluation of the trial. Source data are contained in source documents.

Examples of these original documents, and data records include: hospital records, clinical and office charts, laboratory notes, memoranda, subjects' diaries or evaluation checklists, pharmacy dispensing records, recorded data from automated instruments, copies or transcriptions certified after verification as being accurate and complete, microfiches, photographic negatives, microfilm or magnetic media, x-rays, subject files, and records kept at the pharmacy, at the laboratories, and at medico-technical departments involved in the clinical trial. Source documents are kept in a secure location that is locked and requires approved access.

18.23 Case Report Forms

The study case report form (CRF) is the primary data collection instrument for the study. All data requested on the CRF must be recorded. All missing data must be explained. If a space on the CRF is left blank because the procedure was

not done or the question was not asked, write “N/D”. If the item is not applicable to the individual case, write “N/A”. All entries should be printed legibly in black ink. If any entry error has been made, to correct such an error, draw a single straight line through the incorrect entry and enter the correct data above it. All such changes must be initialed and dated. Do not erase or use “white-out” for errors. For clarification of illegible or uncertain entries, print the clarification above the item, then initial and date it. If the reason for the correction is not clear or needs additional explanation, neatly include the details to justify the correction.

18.24 Records Retention

The investigator will maintain records and essential documents related to the conduct of the study. These will include subject case histories and regulatory documents.

The investigator will retain the specified records and reports for;

1. As outlined in the Mayo Clinic Research Policy Manual –“Retention of and Access to Research Data Policy”

[REDACTED]

19.0 Study Finances

- 19.1 Costs charged to patient: routine clinical care
- 19.2 Tests to be research funded: Venipuncture, DNA analysis, and Biobanking
- 19.3 Other budget notes: The Marley Grant and the Mayo Clinic Radiation Oncology Unit are funding this study and will cover all costs related to running this study

20.0 Publication Plan

The principal investigators hold primary responsibility for publication of the results of this study and approval from the principal investigators must be obtained before any information can be used or passed on to a third party. The principal investigator would maintain control and use of all data used in the study during the study and after the study has been completed.

Appendix I
ECOG PERFORMANCE STATUS

Grade

0	Fully active, able to carry on all pre-disease activities without restriction (Karnofsky 90-100).
1	Restricted in physically strenuous activity but ambulatory and able to carry out work of a light or sedentary nature, e.g., light housework, office work (Karnofsky 70-80).
2	Ambulatory and capable of all self-care, but unable to carry out any work activities. Up and about more than 50 percent of waking hours (Karnofsky 50-60).
3	Capable of only limited self-care, confined to bed or chair 50 percent or more of waking hours (Karnofsky 30-40).
4	Completely disabled. Cannot carry on any self-care. Totally confined to bed or chair (Karnofsky 10-20).
5	Dead

Appendix II
Mayo Breast Patient Survey

Mayo Breast Patient Survey

Survey Date (mm/dd/yyyy):

DIRECTIONS: For each question below, please mark one response that describes how you would rate your symptoms DURING THE PAST DAY.

1. How you would describe...

Your overall quality of life? *Response scale 1 to 10, with 1 = as bad as it could be; 10 = as good as it could be*

The severity of your pain, on average? *Response scale 1 to 10, with 1 = no pain; 10 = Pain as bad as it could be*

Your level of fatigue, on average? *Response scale 1 to 10, with 1 = no fatigue; 10 = fatigue as bad as it could be*

DIRECTIONS: For each question below, please mark one response that describes how you would rate your symptoms IN THE LAST 7 DAYS.

2. **In the last 7 days**, how much did anxiety interfere with your usual or daily activities?

Not at all
A little bit
Somewhat
Quite a bit
Very much

3. **In the last 7 days**, how much did insomnia, including falling asleep, staying asleep, or waking up early INTERFERE with your usual or daily activities?

Not at all
A little bit
Somewhat
Quite a bit
Very much

4. **In the last 7 days**, what was the SEVERITY of your shortness of breath at its WORST?

Not at all
A little bit
Somewhat
Quite a bit
Very much

5. **In the last 7 days**, what was the SEVERITY of your cough at its WORST?

Not at all
A little bit
Somewhat
Quite a bit
Very much

6. **In the last 7 days**, how much did problems with concentration INTERFERE with your usual or daily activities?

Not at all
A little bit
Somewhat
Quite a bit
Very much

7. **In the last 7 days**, how much did sad or unhappy feelings INTERFERE with your usual or daily activities?

Not at all
A little bit
Somewhat
Quite a bit
Very much

8. **In the last 7 days**, what was the SEVERITY of your skin burns from radiation at their worst?

Not at all
A little bit
Somewhat
Quite a bit
Very much

9. **In the last 7 days**, what was the SEVERITY of your difficulty swallowing at its WORST?

Not at all
A little bit
Somewhat
Quite a bit
Very much

10. **In the last 7 days**, how SEVERE have the following problems been (at their WORST)?

Flaking or peeling of the treated breast or chest wall; *response options 0 to 10, 0 = not at all, 10 = flaking as much as could be*

Bleeding of or leaking fluid from the treatment breast or chest wall; *response options 0 to 10, 0 = not at all, 10 = bleeding as much as could be*

Blistering of the treated breast or chest wall; *response options 0 to 10, 0 = not at all, 10 = blistering as much as could be*

Itching of the treated breast or chest wall; *response options 0 to 10, 0 = not at all, 10 = as itchy as it could be*

Skin burns from radiation on your back; *response options 0 to 10, 0 = not at all, 10 = as itchy as it could be*

11. If you had to do it all over again, would you have this **RADIATION** treatment again?

Yes
No

12. Have you been diagnosed with an infection at your breast cancer surgical site that required treatment with antibiotics or surgery?

Yes
 No

We are interested in your evaluation of your physical appearance and functioning. Please rate the following items from 0 to 10, according to how you feel **AT THIS POINT IN TIME**.

Is the color of your treated breast/chest wall skin different than the other side (red, tan, or lighter)? *response options 0 to 10, 0 = not at all, 10 = as different as it could be*

Do you have visible small blood vessels (spider veins) on your treated breast/chest wall?
response options 0 to 10, 0 = not at all, 10 = as many as it could be

Do you have pain with swallowing? *response options 0 to 10, 0 = not at all, 10 = as painful as could be*

Do you have numbness or a tingling sensation in the arm on the side that was treated?
response options 0 to 10, 0 = not at all, 10 = as much as it could be

Do you have tightness, pulling, or stretching in the arm, breast, or chest area (in the side that was treated?) *response options 0 to 10, 0 = not at all, 10 = as much as it could be*

Do you have tenderness or discomfort on the treated breast/chest wall? *response options 0 to 10, 0 = not at all, 10 = as much as it could be*

Overall, how would you rate the cosmetic results of your breast treatment?
 Excellent Good Fair Poor

Please rate the following items according to your evaluation **at this point in time**:

Breast/chest wall texture (hardening)	 None	 Slight	 Moderate	 Large
Arm heaviness	 None	 Slight	 Moderate	 Large
Shoulder movement	 None	 Slight	 Moderate	 Large
Arm movement	 None	 Slight	 Moderate	 Large
Breast/chest wall pain	 None	 Slight	 Moderate	 Large
Ability to lift objects	 None	 Slight	 Moderate	 Large
Fit of shirt sleeve	 None	 Slight	 Moderate	 Large
Breast/chest wall tenderness	 None	 Slight	 Moderate	 Large
Shoulder stiffness	 None	 Slight	 Moderate	 Large
Scar tissue	 None	 Slight	 Moderate	 Large
Shoulder pain	 None	 Slight	 Moderate	 Large
Arm pain	 None	 Slight	 Moderate	 Large
Arm swelling	 None	 Slight	 Moderate	 Large
Breast/chest wall swelling	 None	 Slight	 Moderate	 Large
Arm stiffness	 None	 Slight	 Moderate	 Large
Breast/chest wall sensitivity	 None	 Slight	 Moderate	 Large
Fit of clothing	 None	 Slight	 Moderate	 Large
Axillary (arm pit) fullness or numbness	 None	 Slight	 Moderate	 Large

Please complete the following questions if you had breast conserving therapy or mastectomy with reconstruction.

Please rate the following items according to your evaluation **at this point in time**

Breast size	 None	 Slight	 Moderate	 Large
Nipple appearance	 None	 Slight	 Moderate	 Large
Breast shape	 None	 Slight	 Moderate	 Large
Breast elevation (how high the breast is)	 None	 Slight	 Moderate	 Large
Fit of bra	 None	 Slight	 Moderate	 Large
Breast heaviness	 None	 Slight	 Moderate	 Large

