- 16.531 *Quality of life:* The subscales of the BCTOS, elements from CTCAE-PRO, and other patient reported measures such as fatigue, breast pain, breast shape, and arm related morbidity outlined in the appendix will be summarized as the mean \pm SD and median (minimum value, maximum value). Scale score trajectories over time will be examined using stream plots and mean plots with standard deviation error bars overall. Analysis will include percent change from baseline using t-tests and generalized linear models to test for changes at each time point and non-zero slope respectfully.
- 16.532 *Cosmesis:* The values of the cosmesis instruments (patient self-reported and panel-assessed) will be summarized with the frequencies and confidence intervals of fair or poor cosmesis events at baseline, 2 years, and 5 years.
- 16.533 Tumor mutation signatures will be analyzed before and after radiotherapy as compared to pathologic information at the time of surgery. Continuous variable will be compared using unpaired t tests and monimal variables will be compared using contingency tables and Chi square analyses.
- 16.534 Pathologic changes due to preoperative radiotherapy observed at the time of definitive surgery will be described.

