Appendix III
Mayo Patient Survey PRO-CTCAE Mayo 10

Survey Date (mm/dd/yyyy):

Please answer the following questions about your symptoms.

	Not at all	A little bit	Somewhat	Quite a bit	Very much
In the last 7 days, how much did anxiety INTERFERE with your usual or daily activities:					
In the last 7 days, how much did insomnia including difficulty falling asleep, staying asleep, or waking up early INTERFERE with your usual or daily activities:					
In the last 7 days, how much did decreased appetite INTERFERE with your usual or daily activities:					
	Never	Rarely	Occasionally	Frequently	Almost Constantly
In the last 7 days, how OFTEN did you have nausea:					
	Not at all	A little bit	Somewhat	Quite a bit	Very much
In the last 7 days, how much did shortness of breath INTERFERE with your usual or daily activities:					
In the last 7 days, how much did problems with concentration INTERFERE with your usual or daily activities:					
In the last 7 days, how much did sad or unhappy feelings INTERFERE with your usual or daily activities:					
	None	Mild	Moderate	Quite a bit	Very severe
In the last 7 days, what was the SEVERITY of your constipation at its WORST:					
	Not at all	A little bit	Somewhat	Quite a bit	Very much
In the last 7 days, how much did numbness or tingling in your hands or feet INTERFERE with your usual or daily activities:					
	Never	Rarely	Occasionally	Frequently	Almost Constantly
In the last 7 days, how OFTEN did you have loose or watery stools (diarrhea):					

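### The back-burn line in Appendix II item 10 carries the itch anchor, so its score is ambiguous; four other severity items use the options that Appendix III keeps for interference

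*Combined protocol and SAP*

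**What the plan says.** Appendix II (Mayo Breast Patient Survey), item 10, asks about the last week: "how SEVERE have the following problems been (at their WORST". Five problems follow, each scored 0 to 10. The fourth is "Itching of the treated breast or chest wall; *response options 0 to 10, 0 = not at all, 10 = as itchy as it could be" and the fifth is "Skin burns from radiation on your back; *response options 0 to 10, 0 = not at all, 10 = as itchy as it could be".

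Earlier in the same survey, four questions ask for severity on five worded steps. Item 4 is "what was the SEVERITY of your shortness of breath at its WORST" and item 8 is "what was the SEVERITY of your skin burns from radiation at their worst". Items 5 (cough) and 9 (swallowing) have the same form. The steps run from *not at all* to *very much*.

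Appendix III has one severity question, "In the last 7 days, what was the SEVERITY of your constipation at its WORST". Its steps run from *none* through *mild* and *moderate* to *very severe*, with *quite a bit* in fourth place. Appendix III asks about breathlessness as interference: "how much did shortness of breath INTERFERE with your usual or daily activities".

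Section 16.531 covers the analysis: "The subscales of the BCTOS, elements from CTCAE-PRO, and other patient reported measures such as fatigue, breast pain, breast shape" and similar measures are to be summarised by mean, SD, median and range. It adds trajectory plots, t-tests on percentage change from baseline, and generalized linear models. Sections 2.3 and 16.3 class patient-reported outcomes as exploratory.

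**The concern.** A numeric rating takes its meaning from the question and from the labels at its two ends. On the back-burn line these disagree: the question is about burns, and the upper label is about itch. A patient with a bad burn that does not itch could answer high by following the question or low by following the label. The data file would not show which was meant.

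The four worded items are a milder case. They name the right symptom, but their options describe extent rather than grades of severity. The middle step, *somewhat*, cannot be equated with *moderate* on the severity scale in Appendix III. Two of these items, breathlessness and radiation burns, are natural patient-reported companions to the pneumonitis and dermatitis that clinicians grade under section 10.4, so a reader of the results may want to quote them as severity levels.

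**Working it through.** The plan gives no figure to reproduce here. The check compares what each question asks with what its response labels describe.

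**Step 1. Item 10, line by line (Appendix II).** The stem asks for severity throughout.

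| Line | Problem rated | Symptom named at 10 | Agree? |
|---|---|---|---|
| 1 | Flaking or peeling | Flaking | Yes |
| 2 | Bleeding or leaking | Bleeding | In part: leaking is not named |
| 3 | Blistering | Blistering | Yes |
| 4 | Itching | Itch | Yes |
| 5 | Radiation burns on the back | Itch | No |

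One line of five names a different symptom. Its anchor is word for word that of line 4, which suggests a copying slip.

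**Step 2. The five-step items in Appendix II.** Items 2 to 9 make 8 items, and all use the *not at all* to *very much* options.
- Interference questions: items 2, 3, 6 and 7, so 4. The options fit.
- Severity questions: items 4, 5, 8 and 9, so 4. The options describe extent.
- Check: 4 + 4 = 8.

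**Step 3. The same comparison in Appendix III.** Of its 10 items, 7 ask about interference (anxiety, insomnia, appetite, breathlessness, concentration, sadness, numbness), 2 ask about frequency (nausea, loose stools) and 1 asks about severity (constipation); 7 + 2 + 1 = 10. The *not at all* to *very much* set appears only with the 7 interference items. The severity item has its own set. The two appendices therefore treat severity questions differently, and no outside source is needed to see it.

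**Step 4. What each mismatch costs.**
- Back-burn line (1 item): the score could reflect either symptom.
- Items 4, 5, 8 and 9 (4 items): the steps are ordered, start at no symptom and refer to the symptom asked about, so they still rank burden. What is lost is a clear severity level and comparability with a severity-scaled item.
- Total touched: 1 + 4 = 5 items, of which 1 has a wrong anchor.

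**Step 5. Where the scores are used.** They enter section 16.531 only. Acute and late adverse events (16.521, 16.522) use maximum grades under CTCAE v4.0 (10.2, 10.4). The stopping rule (16.62) counts grade 3 or higher events and worsening on the Harvard cosmesis scale. The primary endpoint is read from the surgical specimen.

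**The case against.** The strongest reply is that this is a one-line slip in an exploratory survey. The stem asks for severity, the line says burns, and a patient can still choose a high number. Item 8 asks about radiation burns in general, and other lines of item 10 cover flaking, blistering and itching of the treated area. The appendix text describes the scales rather than showing the form, and section 18.1 allows surveys to be scanned or entered electronically, so the version patients see may be correct. Section 11.4 says quality of life questionnaires are standard of care; if these surveys are among them, changing options partway could do more harm to within-patient comparisons than the labels do.

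Much of this stands. It limits the size of the point and makes checking the fielded form the first step. It does not remove the conflict on the back-burn line, and item 8 is no full substitute because it is not specific to the back.

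A reader might infer more, and the documents do not support it:
- *Patient-reported toxicity scores in general fail to measure what they claim.* Only one item is anchored to another symptom, and most items fit their scales.
- *A patient with a burn that does not itch has no valid high score.* The anchor is ambiguous, but it does not bar a high answer.
- *The severity and interference versions of breathlessness will be pooled.* Section 16.531 nowhere proposes this, and asking both is not an error.
- *The items depart from the official PRO-CTCAE scales.* The documents do not reproduce those scales, and section 16.3 promises only elements of the instrument.
- *The constipation item is a sixth mismatch.* Its options form an ordered severity scale with one odd label.

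**Conclusion.** The point holds in a narrow form. As printed, the back-burn line in item 10 is ambiguous between burn and itch, and this is an error in a data-collection instrument. Items 4, 5, 8 and 9 are inconsistent with Appendix III but still usable as rankings of the symptom each one names. The effect is confined to exploratory patient-reported results and does not reach the pCR decision, CTCAE-graded toxicity or the stopping rule.

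This rests on the fielded form matching the appendix, which the documents cannot confirm. If the form already carries a burn anchor, the first part reduces to correcting the appendix.

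**What to change.** 1. Check the fielded survey, on paper and on screen, against Appendix II.
2. Re-anchor the back-burn line to burn severity, for example *10 = burns as bad as could be*. Add a form-version flag to the dataset and report answers given on the old anchor separately.
3. Leave items 4, 5, 8 and 9 as worded unless the institution can change them without breaking comparability with baseline surveys.
4. If their wording stays, add a sentence to 16.531: each of these four items is analysed on its own as an ordinal rating (for example, the number of patients in each category at each visit) and is not reported as a severity level comparable with a severity-scaled item.

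The cost is a small form correction, one extra variable and one sentence of analysis plan. If the surveys are shared standard-of-care forms, step 2 also needs institutional agreement. The drawback is that the back-burn data may split into two versions, which in a trial of 25 patients leaves little in each. Step 4 is in the study team's hands even if the form cannot be changed.
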